### **3 Investigational plan**

#### **3.1 Study design**

This will be an international, multicenter, randomized, double-blind, placebo controlled efficacy and safety study recruiting osteoporotic children and adolescents receiving glucocorticoid therapy within the 12 months preceding screening who manifest a LS-BMD Z-score of -0.5 or worse plus evidence of low impact/fragility fracture.

At the baseline visit (Visit 2), patients whose eligibility is confirmed will be randomized to one of two treatment groups. Patients may be hospitalized at the discretion of the investigator for observation following the first study drug infusion. Ionized calcium will be assessed before the first study drug infusion only. Patients will receive the second study drug infusion at the Month 6 visit. Safety and efficacy will be assessed at 6 and 12 months, with additional telephone visits to assess adverse events [REDACTED] and concomitant medication at 3 and 9 months. Renal safety utilizing the Schwartz calculation for GFR will be assessed at screening, and 10 days after the i.v. infusion of study drug 6 and 12 months.

#### **3.2 Rationale for study design**

The patient population will be described in more detail in the [Section 4](#) below.

A placebo control design is being utilized because currently there is no approved therapy to treat children with secondary osteoporosis and there is no clinically accepted off-label gold standard of therapy for this pediatric patient population. In adults, an improvement in BMD can often be achieved with oral administration of calcium and vitamin D ([ACR Task Force 1996](#)). All children enrolled in this study will be provided with conservative intervention to ensure adequate dietary intake of calcium and vitamin D, regardless of their treatment assignment (diet with or without supplements).

#### **3.3 Rationale for dose/regimen, route of administration and duration of treatment**

Zoledronic acid dose selection for Study CZOL446H2337 is based on several sources of information, including safety and efficacy data from completed Novartis clinical trials in adults with postmenopausal osteoporosis, pediatric patients with severe OI, long-term safety in pediatric patients with OI, and a PK study in pediatric patients with severe OI. Published data is available from trials in patients with postmenopausal osteoporosis ([Reid 2002](#); [Black 2007](#)). Adults with benign disease (Paget's and PMO) have received ZOL safely up to 5 mg i.v. by slow injection (over 15 minutes) over various dosing frequencies. Cancer patients have received between 4 and 8 mg i.v. monthly, in long-term studies (> 1 year). In the Novartis ZOL pediatric studies to date, the dose schedule was an infusion of 0.05 mg/kg (max 4 mg) administered quarterly. This dose was extrapolated from a comparison with a pamidronate infusion in patients with tumor-induced hypercalcemia that showed that 4 mg ZOL was more effective than 90 mg pamidronate. The 4 mg dose of ZOL represents an approximate adult dose of ZOL of 0.07 mg/kg or a dose of pamidronate of 1.5 mg/kg for a 60 kg adult. Pamidronate 1.5 or 3.0 mg/kg administered every 6 months was the dose range and interval used in the long-term pamidronate OI study ([Glorieux et al 1998](#)). However, in this trial, the

pamidronate dosing interval was shortened to a 4-month dosing regimen to improve the response in bone markers of disease activity, monitored each month.

Study CZOL446H2202 (see IB) is the largest Novartis-sponsored trial in pediatric patients with metabolic bone disease. This 12-month study compared the efficacy and safety of i.v. zoledronic acid 0.05 mg/kg administered quarterly to i.v. pamidronate 1.0 mg/kg on each of 3 successive days administered quarterly in 155 patients with severe OI. The results showed that ZOL was superior to pamidronate in increasing LS-BMD at Month 12 and in reducing markers of bone turnover, both formation and resorption. Additionally, clinical fracture reduction within treatment was significant overall, and regardless of OI type. The overall incidence rate of adverse events was similar between the two treatment groups. There was no evidence of a long-term effect on renal function following the administration of ZOL in this patient population. The pharmacokinetics of a single infusion of ZOL 0.05 mg/kg, in children aged 3-8 years and 9-17 years, were similar to those observed in adult oncology patients at approximately the same mg/kg dose. Plasma concentrations in the pediatric patients were generally at or below the median concentrations in adults, which may be an advantage in consideration of drug safety and tolerability in children.

In a second trial with OI patients (see IB for study CZOL446H2202E1), the 12-month extension study, long-term safety was assessed in 103 patients receiving 0.05 mg/kg zoledronic acid either as an annual infusion or twice a year (6 months apart). In this study, median increases in LSBMD were approximately 1.3% higher in patients who received the twice yearly dosing of zoledronic acid. Though these data from the extension study should be interpreted with caution as the sample sizes are too small to make definitive conclusions, it is established that there is an effect of puberty on bone degradation, with children demonstrating high bone resorption relative to adults.

Therefore, the zoledronic acid dose and interval selected for this protocol, 0.05 mg/kg as two i.v. infusions at a 6 month interval, is expected to provide superior efficacy (as measured by change in LS-BMD Z-score) compared to placebo in pediatric patients with osteoporosis. The maximum allowable zoledronic acid dose of 5 mg (regardless of patient weight), does not exceed the doses already used in adults and is well within the maximum zoledronic acid dose tested in Phase I Novartis Oncology trials: zoledronic acid 16 mg by slow i.v. infusion. In this study in children with osteoporosis, zoledronic acid will be administered as an i.v. infusion over at least 30 minutes.

### **3.4 Rationale for choice of comparator**

A placebo control has been selected because there is no standard treatment for this condition and although many pediatricians use bisphosphonates to treat fractures in children, the efficacy and safety of bisphosphonate therapy still needs to be determined in a population with secondary osteoporosis.

### **3.5 Purpose and timing of interim analyses/design adaptations**

It is not intended that an interim analysis will be conducted for this study.

## 3.6 Risks and benefits

### Benefit

The potential benefit of zoledronic acid in children at risk of osteoporosis due to underlying disease or intermittent high dose glucocorticoids is outlined below and in the IB.

There is evidence that bisphosphonates have anti-apoptotic effects on osteoblasts and osteocytes which may lead to increased trabecular thickness and thus, may partly explain why bisphosphonates produce a greater reduction in fracture risk than that expected from BMD gains alone (Plotkin 1999). Furthermore, BMD is greatly influenced by sex steroids, and puberty can be delayed in the presence of GC which can also result in short stature which may be offset by the use of bisphosphonates (Glorieux et al 1998).

The most commonly studied bisphosphonate in children has been i.v. pamidronate in the treatment of a primary juvenile osteoporosis, osteogenesis imperfecta (OI). The typical treatment protocol reported in OI is administration of pamidronate on three consecutive days in hospital (Glorieux et al 1998). There is some variation of dosing frequency (typically every 1 to 4 months, depending upon the age of the patient, with younger patients receiving more frequent infusions). Treatment requiring three consecutive days of intravenous therapy every several months can cause a significant burden of both time and cost. The efficacy of cyclic single-day intravenous pamidronate infusions in a heterogeneous group of patients between 6 to 21 years of age was studied and demonstrated similar improvements in bone density and in fracture rate as reported with 3-day infusions in patients with OI (Steelman 2003).

A direct comparison of 2-day pamidronate (PAM) to a 2-day infusion of ZOL has been published in 23 children with OI (Barros et al 2012). Twelve months after treatment, the PAM and ZOL groups average LS-BMD increased by 51.8 % ( $p = 0.053$ ) and 67.6 % ( $p = 0.003$ ), respectively. LS-BMD Z-score for the ZOL group at the end of treatment was higher compared with the PAM group but only a borderline significance ( $p = 0.053$ ). Only mild side effects were reported in both groups and the authors concluded that ZOL was not different from PAM in efficacy and safety in this group of children. More recently, a retrospective study reviewed treatment with PAM and ZOL and followed up the children for up to 2 years (Bowden et al 2015). The authors reported that i.v. bisphosphonate therapy significantly increased BMD and reduced fracture rate during the treatment with a beneficial effect in BMD maintained for 2 years after discontinuation of therapy. A second retrospective study reviewed PAM administered in cycles of 1.5 mg/kg per day over 2 days every 3 months and ZOL as a single dose of 0.05 mg/kg every 6 months to patients aged at least 5 years with type I or IV OI (Saraff et al 2015). Twenty children were identified in each group; LS-BMD Z-scores increased significantly in both groups over 12 months ( $p < 0.001$ ) with no significant differences shown between PAM and ZOL. Another study has been conducted by the sponsor to evaluate the efficacy and safety of ZOL as compared to pamidronate in the treatment of children with severe OI (Study CZOL446H2202 described in IB). The ZOL treated group, had a mean 42.7% increase from baseline in LS-BMD at Month 12 compared with a mean increase of 34.7% in the pamidronate treated group. These changes were consistent with pediatric OI literature which has reported an annualized increase in BMD of 41.9% with cyclical pamidronate (Glorieux et al 1998). The deviation from normal, as measured by the LS-BMD Z-score, at both 6 and 12 months showed an improvement with ZOL. Importantly,

both treatments reduced the occurrence of clinical fractures per patient significantly ( $p < 0.0001$ ) following 12 months of treatment, although the proportion of patients who had clinical fractures in the 12 months of study treatment was similar in the two groups (ZOL: 32 patients, 43.2%; pamidronate: 31 patients, 40.8%; HR 1.05, 95% CI 0.64 – 1.72). Of note, there was a higher risk of clinical fracture in the type I patients treated with ZOL compared to pamidronate (HR 2.12, 95% CI 0.96 – 4.69), and a lower risk of clinical fracture in the type III and IV patients treated with zoledronic acid compared to those patients treated with pamidronate (HR 0.59, 95% CI 0.29 – 1.19).

The evidence of bisphosphonate therapy in children and adolescents with secondary osteoporosis has been reviewed (Ward et al 2007). More recent retrospective studies and reviews on zoledronic acid in children with osteoporosis have been published which report benefits on BMD, bone pain and fractures (Baroncelli and Bertollini 2014, Boyce et al 2014, Brown and Zacharin 2009) and authors agree that prospective randomized controlled trials are still needed to evaluate the benefit risk of bisphosphonates. An increasing number of pediatric metabolic bone experts now reserve bisphosphonate therapy for the management of low bone mass in children and adolescents who have symptoms of a fragility fracture (Boyce and Gafni 2011), and there is one recent publication on the prophylactic use of bisphosphonates in the management of boys with Duchenne muscular dystrophy (DMD) who are receiving long-term glucocorticoids (Sarkozy et al 2014).

## Risks

### Known risks of zoledronic acid

Since this protocol was first written in 2008, there have been more publications on the potential use of bisphosphonates in children with kidney diseases including nephrotic syndrome (Gruppen et al 2013, Sbrocchi et al 2011).

ZOL is concentrated and excreted via the kidney and, like other bisphosphonates, has the potential to produce renal injury. Thus, care should be taken when administering the compound to patients with renal insufficiency. Although case reports have been published in adult medicine regarding the nephrotoxicity of ZOL with an incidence of acute kidney injury (AKI) between 9% and 13%, bisphosphonate-induced, AKI in children remains undocumented (Patzner 2008).

- In this protocol, patients are excluded if they have an estimated GFR  $< 60$  mL/min/1.73 m^2 or a rising serum creatinine increase greater than 0.5 mg/dL (44.2 μmol/L) between Visit 1 and Visit 2. Patients who have nephrotic syndrome with osteoporosis, who do not meet these exclusion criteria, have been stable for 3 months prior to enrollment, and meet the remaining eligibility criteria can be considered for this study.

Post-infusion acute phase reactions are more common after the first infusion and can include pyrexia, muscle and joint pain.

- To reduce the risk of these reactions, children will be instructed to eat and drink as usual, NSAIDs or acetaminophen (paracetamol) will be prescribed and an anti-emetic may be provided to reduce the risk of symptomatic hypocalcemia if the child develops nausea or starts to vomit. Further calcium supplements will be provided for up to 10 days at the time

of infusion and parent/guardian instructions provided on the signs to watch for as well as an emergency number, if needed.

Hypersensitivity reactions including anaphylactic reaction, anaphylactic shock, angioedema, bronchospasm and urticaria are listed in the IB. Therefore, children with a previous known hypersensitivity are excluded. Should a child develop a hypersensitivity reaction, it must be reported as an adverse event.

A rare risk in patients who receive bisphosphonates is osteonecrosis of the jaw (ONJ). This condition has been reported primarily in cancer patients whose complex treatment regimens include higher doses and frequencies of bisphosphonates, typically administered with other treatments such as radiation, chemotherapy and glucocorticoids. To date and to the best of our knowledge, ONJ has not been reported in the literature in children or adolescents who have received bisphosphonates. Based on available evidence, a causal relationship between ONJ and bisphosphonates, including ZOL, has not been established.

- In this study a lower dose and short duration of zoledronic acid is used than has been reported in cases of ONJ in adults, and all children will have an examination of their oral cavity during the study and referred to a dentist if necessary.

#### **Potential risks of zoledronic acid in a pediatric population**

Based on the results from animal studies showing inhibition of bone calcification by first generation bisphosphonates (Mashiba 2001), there are theoretical concerns about negative effects on growth in children. In growing children, each bisphosphonate treatment cycle leads to the accumulation of a thin band of mineralized tissue at the interface between growth plate and metaphysis which is evident as a metaphyseal line on the radiograph (Land et al 2006a). These lines represent persistent calcified cartilage in the horizontal trabeculae which later remodels into secondary bone. This interface between weaker bone and stronger bisphosphonate-treated bone could represent a site for potential fracture. However, in clinical trials with i.v. bisphosphonates, linear growth in children and adolescents has not been observed to be negatively impacted with no observed increase in fracture. To the contrary, cyclical i.v. treatment with pamidronate has been shown to be beneficial in children with severe forms of OI (Glorieux et al 1998).

- To investigate this potential risk, a placebo control is used for comparison; all patients will have DXA examination at 6 and 12 months and in the event of clinical worsening or diagnosis of new fracture, an X-ray will be performed.

Another concern in children is effects on the reproductive organs. The animal reproduction studies of zoledronic acid are described in the Investigator's Brochure. Teratogenicity was observed in the rat, but not the rabbit when treatment during the perinatal period resulted in delayed parturition likely resulting from the calcium lowering effect of the compound outside of bone, which negatively affects uterine contraction. There were no effects reported in males.

- Consequently this protocol requires contraception in all girls who are pubertal and may become pregnant and in some countries additional pregnancy checks will be made.

There are potential concerns regarding the i.v. infusion in children. Apart from the potential risks at the infusion site of pain, infection, phlebitis, hematoma and extravasation, the infusion may also cause fluid overload if the rate is too high and this can result in hypertension, heart

failure or pulmonary edema. Additional risks of the infusion can include electrolyte imbalance and embolism.

- The infusion is administered in a hospital or clinic by staff experienced in administering i.v. infusions to children. The infusion line is flushed with saline before and after administration and the infusion given over at least 30-minutes e.g. in a 25 kg child, 100 mL may be administered over one hour at a rate of 5 mL/minute.

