#### **Protocol procedures: blood draws and radiology**

The number of blood draws and frequency of hospital visits in this protocol is within the usual limit of clinical practice for children with these serious underlying diseases. The radiation exposure is increased over routine clinical practice, but within the limits for children who have suffered a fracture and no greater than the exposure during a transatlantic flight. Repeat blood draws and X-rays/DXA will only be requested when absolutely necessary i.e. safety, baseline or end-of-study visits.

In summary, the risks to the children and adolescents in this trial will be minimized by compliance with the eligibility criteria and study procedures, particularly adequate hydration at the time of the infusion, adherence to a diet rich in calcium and vitamin D, regular renal monitoring and contraception in girls of child bearing potential. A maximum dose of 5 mg zoledronic acid (regardless of patient weight) and a minimum 30 minute infusion time 6-monthly are designed to reduce the risk of possible adverse effects. This dose regimen has been used in children with primary and secondary osteoporosis and has shown a favorable risk-benefit profile.

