### 5.2 Treatment arms

At Visit 1, all patients will be counselled regarding adequate dietary intake of calcium and vitamin D with or without supplementation. At Visit 2, each patient will be randomized in a

1:1 ratio within one of two treatment arms to receive either twice yearly 0.05 mg/ kg (max 5mg) i.v. infusion (at least 30 minutes) of zoledronic acid at randomization and Month 6 or twice yearly i.v. placebo at randomization and Month 6.

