### 5.5.4 Instructions for prescribing and taking study treatment

All kits of study treatment assigned by the IRT will be recorded/databased in the IRT.

Patients will receive a single dose of zoledronic acid or placebo of 0.05 mg/ kg, administered as a slow infusion of 100 mL over at least 30 minutes, at Visit 2 and Visit 5 as follows:

AGE	DOSE of ZOLEDRONIC ACID	TIME OF INFUSION
≥ 5 years to ≤ 17 years	0.05 mg/kg diluted in 100 mL of NS	30 minute infusion

The zoledronic acid or placebo dose is not to exceed 5.0 mg

A peripheral intravenous line must be used for the ZOL or placebo infusion. The i.v. infusion will be preceded by and followed by a 10 mL normal saline flush of the intravenous line.

As an example, the following table demonstrates how to prepare drug for a patient who weighs 46 kg.

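### The only infusion rate the protocol prints (section 3.6) contradicts its own one-hour duration and breaks the 30-minute minimum stated in the same sentence

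*Protocol*

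**What the plan says.** Protocol section 3.6, under potential risks in a pediatric population, warns that "the infusion may also cause fluid overload if the rate is too high". The bullet that answers this risk has experienced staff give the infusion in a hospital or clinic, with "the infusion given over at least 30-minutes". It then gives a worked example: "in a 25 kg child, 100 mL may be administered over one hour at a rate of 5 mL/minute".

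The 30-minute minimum recurs elsewhere in the protocol:

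- Section 3.6, closing summary: "a minimum 30 minute infusion time 6-monthly are designed to reduce the risk of possible adverse effects" (said of the minimum together with the 5 mg cap).
- Section 3.3: "zoledronic acid will be administered as an i.v. infusion over at least 30 minutes".
- Section 5.2: "i.v. infusion (at least 30 minutes) of zoledronic acid at randomization and Month 6".
- Section 5.5.4: "administered as a slow infusion of 100 mL over at least 30 minutes, at Visit 2 and Visit 5 as follows".

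On volume, the dosing row in section 5.5.4 reads "0.05 mg/kg diluted in 100 mL of NS". Table 5-2 adds the drug volume to 100 mL of saline and shows 146 mL in total for a 46 kg patient. Neither the protocol nor the SAP gives any other rate in mL/minute.

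**The concern.** Volume, duration and rate are tied by one identity, so any two fix the third. Here the stated rate disagrees with the stated duration. It also disagrees with the minimum that the example is meant to illustrate.

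The place matters. The protocol names too fast a rate as a hazard, offers the 30-minute minimum as a protection, and then prints a rate that breaks it. Someone who times the infusion will comply. Someone who sets a pump from the only rate in the document will infuse too fast.

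There is a related conflict over volume. Section 5.5.4 calls for an infusion of 100 mL, whereas Table 5-2 always prepares more than that. A site that took the 100 mL literally would leave part of the weight-based dose in the container.

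**Working it through.** **Inputs**

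- Section 3.6 example: 25 kg, 100 mL, 60 minutes, 5 mL/minute.
- Minimum duration: 30 minutes (sections 3.3, 3.6, 5.2 and 5.5.4).
- Dose 0.05 mg/kg, maximum 5 mg; drug solution 5 mg/100 mL, i.e. 0.05 mg/mL (sections 5.1.1 and 5.5.4).
- Prepared volume: 100 mL saline plus drug volume (Table 5-2).
- Line flush: 10 mL before and 10 mL after (section 5.5.4).

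**Prepared volume at weight W kg.** Drug volume = 0.05 × W / 0.05 = W mL, capped at 100 mL, so the total is 100 + W mL. At 46 kg this gives 146 mL, which reproduces Table 5-2. At 25 kg it gives 125 mL (1.25 mg in 25 mL of drug solution). At the 5 mg cap it gives 200 mL.

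**Trying to reproduce 5 mL/minute (rate = volume / time), 25 kg child**

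| Volume | Over 60 min | Over 30 min (fastest allowed) | Time at 5 mL/min |
|---|---|---|---|
| 100 mL (as stated) | 1.67 mL/min | 3.33 mL/min | 20 min |
| 125 mL (Table 5-2) | 2.08 mL/min | 4.17 mL/min | 25 min |
| 120 mL (100 + both flushes) | 2.00 mL/min | 4.00 mL/min | 24 min |
| 145 mL (125 + both flushes) | 2.42 mL/min | 4.83 mL/min | 29 min |

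No combination gives 5 mL/minute, and none reaches 30 minutes at that rate. One hour at 5 mL/minute would deliver 5 × 60 = 300 mL.

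**Size of the discrepancy**

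- Against the stated hour: 5 / 1.67 = 3.0 times too fast for 100 mL; 5 / 2.08 = 2.4 times for 125 mL.
- Against the 30-minute ceiling: 5 / 3.33 = 1.50, or 50% over, for 100 mL; 5 / 4.17 = 1.20, or 20% over, for 125 mL.
- By weight at 25 kg: 5 × 60 / 25 = 12 mL/kg/hour. For 125 mL the figures are 125 / 25 = 5 mL/kg/hour over one hour and 250 / 25 = 10 mL/kg/hour at the 30-minute minimum.

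**If the rate were reused at other weights.** Time = (100 + W) / 5 minutes, which reaches 30 only when W is 50 kg or more. The 46 kg patient in Table 5-2 would take 146 / 5 = 29.2 minutes.

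**Which figure is wrong.** 100 mL over one hour respects the minimum; the rate conflicts with both the hour and the minimum. The rate is therefore the faulty figure. The documents do not show what rate was intended.

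**Volume conflict, only if 100 mL is taken literally.** The fraction of the dose delivered would be 100 / (100 + W):

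- 25 kg: 100 / 125 = 80%, i.e. 1.00 of 1.25 mg.
- 46 kg: 100 / 146 = 68%, i.e. 1.58 of 2.3 mg.

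If the whole prepared volume is infused, the fraction is 100%. That is evidently what is meant: the dose is ordered per kg, the dosing row describes dilution in 100 mL of saline, Table 5-2 totals the full prepared infusion, and section 5.5.5 forbids dose adjustments.

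**The case against.** The best defence concerns consequence; the arithmetic is not in dispute. The rate is an illustration in a risk narrative. The operative instructions in section 5.5.4 state the 30-minute minimum correctly, and the faulty sentence itself carries both that minimum and a one-hour duration. Experienced staff would have to overlook all of this to infuse in 20 minutes. The documents give no rate threshold for fluid overload, and section 3.3 reports adults receiving up to 5 mg over 15 minutes. Start and stop times are recorded (section 6.3), and infusion duration is summarized (section 9.3.1 and the SAP's exposure section).

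These points stand as limits. They rule out any claim about the size of harm. Recorded times, however, reveal a short infusion only after it has happened.

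Three narrower objections also have some force. The 46 kg and 50 kg figures extend an example that the protocol confines to a 25 kg child; they show how far the rate fails to generalize and nothing more. The underdose figures belong to a reading that the rest of section 5.5 contradicts, so the 100 mL is a wording conflict rather than a dosing error. Finally, the smallest repair would keep 100 mL and print about 1.7 mL/minute. That would make the sentence consistent with itself but leave it at odds with the 125 mL that Table 5-2 prepares for the same child.

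**Conclusion.** The concern holds. The section 3.6 example contradicts itself: its rate gives 20 minutes against a stated hour, and it breaks the 30-minute minimum in the same sentence. With the volume that Table 5-2 implies for that child, the infusion takes 25 minutes and still falls short. The 20-minute result needs only the three printed numbers. The 25-minute result assumes that the Table 5-2 formula applies at 25 kg, as its general row says.

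This should be corrected, because it is the only rate printed and it is offered as part of the answer to a rate-related hazard in children. No size of harm is claimed. The sample size, the primary analysis and the Z-score difference are not affected. The 100 mL in section 5.5.4 is a secondary wording conflict; it would matter only at a site that stopped the infusion at 100 mL.

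**What to change.** 1. In section 3.6, replace the example with: for a 25 kg child, 125 mL over one hour at about 2.1 mL/minute. Add that the 30-minute minimum allows at most about 4.2 mL/minute for this volume. The sponsor should confirm the intended duration.
2. In section 5.5.4, state that the weight-based dose is added to 100 mL of normal saline and that the entire prepared volume is infused over at least 30 minutes.

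The cost is two wording corrections in the protocol. No patients, visits, procedures or analyses are added.
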